6.9.2 Analysis of other endpoints

All other endpoints will be summarized using the ITT population.

6.9.2.1 Continuous endpoints

Continuous endpoints such as change from baseline and/or percent change from baseline in EASI, DLQI score, SCORAD score, BSA involvement, POEM score will be summarized descriptively by visit and treatment group.

In the analyses of change from baseline and percent change from baseline above Part II baseline will be used for the groups Placebo/SCD-044 █ mg and Placebo/SCD-044 █ mg, while Part I baseline will be used for the other treatment groups.

Continuous endpoints will also be summarized with a Mixed Model for Repeated Measures (MMRM) that will include fixed effects for treatment, visit (time variable), treatment by visit interaction, baseline vIGA score, gender, prior biologic therapy (yes/no), and Baseline value as a covariate. Unstructured covariance matrix will be assumed and Kenward-Roger method for computing the denominator degrees of freedom will be used. If the model fails to converge with the unstructured covariance matrix, the following covariance matrix types will be tried in order until convergence is achieved: heterogeneous Toeplitz (TOEPH), heterogeneous first-order auto-regressive (ARH(1)), Toeplitz (TOEP), first-order auto-regressive (AR(1)), compound symmetry (CS). Data up to Week 16 will be used in this analysis. The model will

be used to estimate treatment LS Means of the endpoint at Week 16 as well as LS mean differences for each SCD-044 dose vs. Placebo with 95% confidence interval and p-value for the hypothesis of no difference. These analyses will be considered supportive.

Percent reduction from baseline in EASI will be presented graphically.

Notes of scoring:

1. EASI.
 - a. Based on gross morphological findings, scores are assigned on a 4-point scale ['0' (absent), '1' (mild), '2' (moderate) and '3' (severe)] for each clinical sign (erythema, induration/papulation, excoriation and lichenification) in four body regions (head/neck, trunk, upper extremities and lower extremities).
 - b. The score of percent of body surface is affected with atopic dermatitis in each body region ranges from 0 to 6.
 - c. Clinical sign scores are summed within each body region and the sum is multiplied by the affected body surface score to arrive at the body region score.
 - d. The total EASI score is the weighted sum of the body region scores:
$$\text{Total EASI score} = 0.1 * \text{head/neck} + 0.3 * \text{trunk} + 0.2 * \text{upper extremities} + 0.4 * \text{lower extremities}$$
It ranges from 0 to 72, with higher scores denoting more severe extent of atopic dermatitis.
2. DLQI. The scoring of each question is as follows: Very Much or Yes = 3, A lot = 2, A little = 1, Not relevant or Not at all or No = 0. The DLQI is calculated by summing the score of each question resulting in a maximum of 30 and a minimum of 0. The higher the score, the more quality of life is impaired.
3. SCORAD.
 - a. Area (A): the extent affected by eczema is determined using the Rule of Nines as a percentage of the whole body, which has a possible maximum of 100%.
 - b. Intensity (B): the intensity of each of the 6 signs is assessed as none (0), mild (1), moderate (2) or severe (3). Total intensity score (B) is calculated by summing the score of each sign resulting in a maximum of 18.
 - c. Subjective symptoms (C): itch and sleeplessness scored by the patient or relative using a visual analogue scale where 0 is no itch (or no sleeplessness) and 10 is the worst imaginable itch (or sleeplessness). These scores are added to give total subjective symptoms score 'C' (maximum 20).
 - d. The total SCORAD score is calculated as: [REDACTED]
4. POEM. Questionnaire consists of 7 items about their atopic dermatitis over the past week. Each of the seven questions carries equal weight and is scored from 0 to 4. The total score is the sum of all items scores (maximum 28), with higher POEM scores denoting more severe eczema. If one question is left unanswered this is scored 0 and the scores are summed and expressed as usual out of a maximum of 28. If two or more questions are left unanswered the questionnaire is not scored.

6.9.2.2 Binary endpoints

Binary endpoints include:

- EASI50, EASI75, EASI90, EASI100 responses (i.e., reduction of at least 50%, 75%, 90% and 100% from baseline in EASI)
- vIGA response (achieving vIGA score of “clear” or “almost clear” on a 5-point vIGA scale with at least two-grade reduction from baseline)
- achieving ≥ 4 -point or ≥ 3 -point improvement in the severity of itching recorded in PP-NRS from baseline
- SCORAD50 and SCORAD75 responses (i.e., reduction of at least 50% and 75% from baseline in total SCORAD score)
- achieving ≥ 4 -point or ≥ 3 -point improvement in the frequency of itching recorded in PP-NRS from baseline
- achieving PGIC improvement
- achieving DLQI total score 0 or 1 at Weeks 16 and 32

Note that for all binary endpoints above that involve change from baseline or percent change from baseline, Part II baseline will be used for the groups Placebo/SCD-044 █ mg and Placebo/SCD-044 █ mg, while Part I baseline will be used for the other treatment groups.

Number and percentage of subjects achieving these endpoints will be presented by treatment group along with 95% confidence interval for percentages based on binomial proportion.

The percentage of subjects achieving EASI75, EASI50, vIGA and SCORAD75, SCORAD50 responses will be presented graphically.

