6.1.4 Peak Pruritus Numeric Rating Scale (PP-NRS)¹⁸

At the study visits [REDACTED] subjects will be asked to assess severity of itching caused due to atopic dermatitis [REDACTED]
[REDACTED]
[REDACTED]

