6.1.5 Validated Investigator Global Assessment (vIGA)¹⁹

At Screening and Baseline, to be eligible for inclusion in the study, subjects must have a definite clinical diagnosis of atopic dermatitis of at least moderate severity [REDACTED] as an overall assessment of all atopic dermatitis lesions.

At the Screening and the study visits [REDACTED] the investigator will perform an overall assessment of all atopic dermatitis lesions [REDACTED]
[REDACTED]
[REDACTED]

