17. The occurrence of all AEs & AESIs will be assessed and documented following the procedures in Sections 5.9, 10.1, and 10.3.

18. The overall status of the Subject's atopic dermatitis will be assessed using the validated Investigator Global Assessment scale for Atopic Dermatitis (vIGA). (See Section 6.1.5). [REDACTED]

19. Eczema Area and Severity Index (EASI) will be evaluated. [REDACTED]

20. Body Surface Area (BSA) involvement will be assessed. [REDACTED]

7.1.2 [REDACTED] Baseline Visit [REDACTED]

If the Screening assessment was completed more than 2 weeks prior:

1. A physical examination will be performed. At a minimum, the physical examination will include the following: height, weight, assessment of general appearance, comprehensive skin examination, HEENT, heart, lungs, musculoskeletal system, lymph nodes, neurological systems, abdomen, and extremities. (See Section 5.2)
2. A urinalysis dipstick will be performed and evaluated at a site (See Section 5.5)
3. A blood sample(s) will be collected for Hematology, Lipid Profile, Chemistry, and Coagulation (See Section 5.5)

The following procedures will be performed at Baseline:

4. Compliance with the inclusion and exclusion criteria, including results of laboratory evaluations, a pulmonary function test, and an ophthalmologic examination will be reviewed.
5. A urine pregnancy test will be conducted for all females of childbearing potential (see Section 5.5)
6. After confirming the eligibility, the Subject will be assigned a randomization number using Interactive Response Technology (IRT). (see Section 8.4.1)
7. The Subject's diary provided at the previous visit will be collected and reviewed.
8. A medical history will be updated with any changes of the Subject's health since the previous study visit. (See Section 5.1)
9. The use of concomitant medications since the previous study visit will be documented and assessed. (See Section 5.8)
10. A [REDACTED] sample will be collected for [REDACTED] sample (See Section 6.3)
11. The occurrence of all AEs & AESIs will be assessed and documented following the procedures in Sections 5.9, 10.1, and 10.3.
12. A query for PML (progressive multifocal leukoencephalopathy) will be performed (See Section 5.10)
13. A query for PRES (Posterior reversible encephalopathy syndrome) will be performed (See Section 5.11)
14. Subject Reported Assessments will be collected for:
[REDACTED]
15. Focused Area Assessments will be performed for:

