6. STATISTICAL METHODS OF ANALYSIS

6.1 General Principles

The statistical analyses will be performed by [REDACTED] with approval of the Sponsor, using SAS® Version 9.4 (or higher). All tables, figures and listings will be produced in landscape format.

In general, all data will be listed by subject and visit/time point where appropriate. The summary tables will be stratified by, or have columns corresponding to, treatment groups.

The total number of subjects in the treatment group (N) under the specified population will be displayed in the header of summary tables.

Data will be summarized using descriptive statistics for continuous variables. Unless otherwise specified, descriptive statistics will include number of subjects, mean, standard deviation, minimum, median, and maximum. Number of subjects with missing values will also be displayed, but only if non-zero. The minimum and maximum statistics will be presented to the same number of decimal places as the original data. The mean and median will be presented to one more decimal place than the original data. The standard deviation will be presented to two more decimal places than the original data.

In summary tables of categorical variables, counts and percentages will be displayed. The count [n] indicates the actual number of subjects in a particular category, which should always be less than or equal to the total number of subjects in the respective study group with known (non-missing) category [M]. Percentage will be obtained by: % = $n/M*100$. Unless otherwise specified, all percentages will be expressed to one decimal place.

All statistical tests will be two-sided at a significance level of $\alpha = 0.05$, unless otherwise indicated.

Baseline will be defined as the last assessment, scheduled or not, prior to the first dose of the study drug, unless otherwise specified. This notion of baseline will also be referred to as Part I baseline. Part II baseline will be defined as the last assessment, scheduled or not, prior to the first dose of the study drug in Part II. Part II baseline will be used in analysis of findings collected in Part II for subjects initially randomized to Placebo and re-randomized to SCD-044

(█ mg or █ mg) in Part II. Throughout this SAP, if the word “baseline” is used without qualification “Part I” or “Part II”, it will refer to Part I baseline.

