6.9.2.4 Time to EASI75, EASI90, vIGA, and PP-NRS responses

Time to achieve EASI75 and EASI90, and time to achieve vIGA and PP-NRS responses will be summarized separately for the Part I of the study, for the Part II for subjects re-randomized at Week 16 and for the study overall for subjects assigned to SCD-044 at the Baseline.

In the analysis of Part I subjects will be analyzed by treatment groups based on the treatment that the subject received in Part I (see [Section 6.1.1](#)). Time to achieve EASI75 will be defined as the number of weeks from the day of the first dose of the study drug to the first EASI assessment in Part I (i.e., up to and including Week 16 visit) when EASI75 is achieved. For subjects who never achieve EASI75 in Part I the time will be censored at the last EASI assessment in Part I. Similar algorithm is used to define time to achieve EASI90.

Similarly, time to achieve vIGA response in Part I will be defined as the number of weeks from the day of the first dose of the study drug to the first vIGA assessment in Part I (i.e., up to and including Week 16 visit) when vIGA score of ‘clear’ or ‘almost clear’ with at least two-grade reduction from Baseline is achieved. For subjects who never achieve vIGA response in Part I the time will be censored at the last vIGA assessment in Part I.

Similarly, time to achieve PP-NRS response in the severity of itching in Part I will be defined as the number of weeks from the day of the first dose of the study drug to the first PP-NRS assessment in Part I (i.e., up to and including Week 16 visit) when severity of itching recorded in PP-NRS with at least four-point (or at least three-point) reduction from Baseline is achieved. For subjects who never achieve PP-NRS response in Part I the time will be censored at the last PP-NRS assessment in Part I.

The analysis for Part II will be conducted only for subjects who were initially randomized to placebo and switched to active treatment in Part II. In this analysis subjects will be analyzed by treatment groups based on their treatments in Part II (see [Section 6.1.1](#)). Times will be defined similarly to the analysis of Part I, except they will start at the time of the switch to a new treatment in Part II and will be censored at the last assessment in the study. Part II baseline will be used when determining EASI and vIGA responses.

[figure not shown]

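### Itch responder rates set no minimum baseline score, so subjects who cannot reach the 4-point or 3-point threshold count as non-responders; this is clearest for placebo switchers in Part II

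*SAP*

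**What the plan says.** SAP 6.9.2.2 lists as binary endpoints a 4-point or 3-point "improvement in the severity of itching recorded in PP-NRS from baseline" and, separately, a 4-point or 3-point "improvement in the frequency of itching recorded in PP-NRS from baseline". Neither carries a minimum baseline score, and the visible text of SAP 4.3 and of the protocol's endpoint lists adds none. The output is a count, a percentage and a binomial 95% confidence interval per treatment group.

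For the analysis set, SAP 6.9.2 states: "All other endpoints will be summarized using the ITT population". SAP 6.1 takes percentages over all subjects in the group whose category is known, and SAP 6.1.3 applies no imputation to these endpoints.

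SAP 6.9.2.4 defines time to itch response, for severity only, as the time until "severity of itching recorded in PP-NRS with at least four-point (or at least three-point) reduction from Baseline is achieved". Subjects who never respond are censored at their last PP-NRS assessment.

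On baseline, SAP 6.9.2.2 gives the two Placebo/SCD-044 groups the Part II baseline and the other groups the Part I baseline. SAP 6.1 defines the Part II baseline as the last assessment before the first Part II dose. For Part II time to response, SAP 6.9.2.4 names the Part II baseline for EASI and vIGA but does not mention PP-NRS.

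Protocol Appendices VIIIa and VIIIb show both itch items on a 0 to 10 scale.

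**The concern.** A baseline of 0 to 3 cannot fall by 4 points, and a baseline of 0 to 2 cannot fall by 3. Such a subject has a known category, non-response, and so stays in the denominator whatever the treatment does. In the time-to-response analysis the same subject stays in the risk set with no possible event, which moves the quartiles later or leaves them unreached.

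The rate as defined therefore mixes two things: how often treatment produces the improvement, and how many subjects had enough itch to show it. In a dose-ranging study the itch rates will be read side by side across doses and across the five Part II groups. The mix makes each rate lower and harder to interpret. It can also create apparent differences between groups that differ only in the share able to respond.

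**Working it through.** The documents give no itch response rate, no baseline PP-NRS distribution and no planned power for these endpoints, so there is no stated figure to reproduce. All values of q and all response rates below are assumptions.

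**Group sizes.** About 240 subjects (protocol 4.1) at 3:1:1:3 (SAP 3.1) give 240 × 3/8 = 90 and 240 × 1/8 = 30, that is 90/30/30/90.

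**Dilution.** Reported rate = (1−q) × rate among those able to respond. With equal q in two arms, the difference shrinks by the same factor and the ratio of rates does not change.

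| q | active, 40% if able | placebo, 20% if able | difference | ratio |
|---|---|---|---|---|
| 0 | 40% | 20% | 20 points | 2.0 |
| 10% | 36% | 18% | 18 points | 2.0 |
| 20% | 32% | 16% | 16 points | 2.0 |

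**Unequal q.** If two arms share a true 30% rate but q is 10% in one and 20% in the other, the reported rates are 0.30 × 0.90 = 27% and 0.30 × 0.80 = 24%. That is a 3-point gap with no treatment difference. Chance imbalance of this kind is most likely in the 30-subject arms.

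**Part II.** Suppose 40% of those able to respond do so in both a switch group and a continuing group, with q = 20% for switchers (reset baseline) and q = 0 for the continuing group. The reported rates are 32% and 40%, so 8 points come from the denominator alone.

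**Time to response.** Ignoring dropout, the reported curve cannot rise above (1−q) times the proportion of able subjects who respond. Reaching the first quartile then needs 25%/(1−q) of able subjects to respond: 25/0.9 = 27.8% at q = 10% and 25/0.8 = 31.3% at q = 20%.

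**Illustrative power.** No such test is planned. For 90 v 90 randomized, two-sided 0.05, normal approximation with pooled variance under the null:
- q = 10%: all subjects (36% v 18%, n = 90) 78.1%; restricted (40% v 20%, n = 81) 79.9%.
- q = 20%: all subjects (32% v 16%, n = 90) 71.3%; restricted (40% v 20%, n = 72) 75.0%.

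**Precision cost of restricting, 30-subject arm.** Half-width = 1.96 × √(p(1−p)/n).
- q = 10%: p = 0.36, n = 30 gives 17.2 points; p = 0.40, n = 27 gives 18.5 points.
- q = 20%: p = 0.32, n = 30 gives 16.7 points; p = 0.40, n = 24 gives 19.6 points.

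**Could an entry criterion set q to zero?** Inclusion criterion 3 in protocol 4.2, which defines moderate to severe disease at Screening and Baseline, is not visible. The readable text gives weak signs against an itch minimum:
- The vIGA section says "to be eligible for inclusion in the study, subjects must have a definite clinical diagnosis of atopic dermatitis of at least moderate severity", and the BSA and EASI sections have similar eligibility wording. The visible part of protocol 6.1.4 says only that "subjects will be asked to assess severity of itching caused due to atopic dermatitis".
- The visible efficacy items at Screening (protocol 7.1.1) are vIGA, EASI and BSA.

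These signs do not settle the matter for Part I. For Part II they are beside the point, because a criterion applied at Screening and Baseline does not constrain the score before the first Part II dose.

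**The case against.** **The Part I premise rests on redacted text.** A reader might infer from the Screening list and from protocol 6.1.4 that there is no itch minimum. The documents do not support that. Criterion 3 is hidden, 6.1.4 is blacked out after one sentence, and the Screening list ends in a redaction. The list may be incomplete: Baseline item 7 collects a diary given at the previous visit, yet no visible Screening item dispenses one. If criterion 3 requires a PP-NRS of at least 4, Part I severity is not diluted at all. This objection stands for Part I severity. It does not reach the reset Part II baseline, and it covers the frequency item only if that item has its own minimum.

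**No comparison is planned.** SAP 6.9.2.2 gives rates with intervals, the time-to-response analysis gives quartiles, and SAP 6.1.2 makes any p-values nominal with no inference drawn. This stands, so the power figures only show scale, and the gain they show is about 2 to 4 points. Because percentages use known categories without imputation, 90 is also an upper limit on the denominator.

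**The all-subject rate is legitimate.** It matches the protocol's endpoint wording and the ITT set, and baseline PP-NRS is already summarized under SAP 6.3, so an imbalance in severity would be seen. This stands as a reason to keep the all-ITT row. It does not make that row sufficient, since a baseline summary does not show what the response rate is among those able to respond.

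**Restriction does not repair Part II comparisons.** Switchers and continuing subjects differ in baseline definition and in treatment history, and the switchers' baseline is measured after the first randomization. This stands in full.

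**Conclusion.** The point holds as a cheap improvement to non-key secondary endpoints. As written, subjects below the threshold are certain non-responders in SAP 6.9.2.2 and stay censored in 6.9.2.4, and the descriptive rates fall by the factor 1−q. That follows from the 0 to 10 scale, the ITT set and the denominator rule. The size is unknown because q is not given; at an assumed q of 10% to 20% the rates lose one tenth to one fifth of their value.

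For Part I severity, q may be zero. For placebo switchers in Part II no entry criterion protects the endpoint, and the frequency item may be exposed in both parts.

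Three stronger readings are not supported. The documents do not show that Part I is diluted. They plan no between-group test on these endpoints, so there is no loss of planned power. Nothing here affects the primary or key secondary results, and it is dilution, not type I error inflation.

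The baseline for Part II time to PP-NRS response is also unclear. SAP 6.1 has a general rule pointing to the Part II baseline for switchers, but it also says that unqualified baseline means Part I, and 6.9.2.4 names only EASI and vIGA.

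**What to change.** In SAP 4.3 and 6.9.2.2, report each itch response among ITT subjects whose applicable baseline is at or above the threshold (at least 4 for the 4-point response, at least 3 for the 3-point response). Do this for severity and for frequency, using the Part II baseline for switchers. Show the number excluded per arm, and keep the all-ITT row, which matches the protocol wording, beside it. In Part I the restriction uses a pre-treatment value, so the randomized comparison is preserved.

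In SAP 6.9.2.4, apply the same restriction to time to PP-NRS response, and state that the Part II baseline applies to PP-NRS as well as to EASI and vIGA.

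Record the change in SAP section 8, which now reports only expanded handling of intercurrent events. Do not present the restricted rates as making switch and continuing groups comparable.

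The cost is SAP wording, a denominator flag for each threshold and item, an extra table row and the section 8 entry. The restricted rows have a smaller n and somewhat wider intervals: in a 30-subject arm, half-widths of roughly 18 to 20 points against about 17 at q of 10% to 20%.

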6.9.2.3 Categorical endpoints

Categorical endpoints include vIGA, PGIC, and PGIS. Number and percentage of subjects with each category of response will be presented by treatment group and visit. Additionally, for vIGA, PGIS shifts from baseline to each post-baseline visit will be presented.

6.9.2.4 Time to EASI75, EASI90, vIGA, and PP-NRS responses

Time to achieve EASI75 and EASI90, and time to achieve vIGA and PP-NRS responses will be summarized separately for the Part I of the study, for the Part II for subjects re-randomized at Week 16 and for the study overall for subjects assigned to SCD-044 at the Baseline.

In the analysis of Part I subjects will be analyzed by treatment groups based on the treatment that the subject received in Part I (see [Section 6.1.1](#)). Time to achieve EASI75 will be defined as the number of weeks from the day of the first dose of the study drug to the first EASI assessment in Part I (i.e., up to and including Week 16 visit) when EASI75 is achieved. For subjects who never achieve EASI75 in Part I the time will be censored at the last EASI assessment in Part I. Similar algorithm is used to define time to achieve EASI90.

Similarly, time to achieve vIGA response in Part I will be defined as the number of weeks from the day of the first dose of the study drug to the first vIGA assessment in Part I (i.e., up to and including Week 16 visit) when vIGA score of ‘clear’ or ‘almost clear’ with at least two-grade reduction from Baseline is achieved. For subjects who never achieve vIGA response in Part I the time will be censored at the last vIGA assessment in Part I.

Similarly, time to achieve PP-NRS response in the severity of itching in Part I will be defined as the number of weeks from the day of the first dose of the study drug to the first PP-NRS assessment in Part I (i.e., up to and including Week 16 visit) when severity of itching recorded in PP-NRS with at least four-point (or at least three-point) reduction from Baseline is achieved. For subjects who never achieve PP-NRS response in Part I the time will be censored at the last PP-NRS assessment in Part I.

The analysis for Part II will be conducted only for subjects who were initially randomized to placebo and switched to active treatment in Part II. In this analysis subjects will be analyzed by treatment groups based on their treatments in Part II (see [Section 6.1.1](#)). Times will be defined similarly to the analysis of Part I, except they will start at the time of the switch to a new treatment in Part II and will be censored at the last assessment in the study. Part II baseline will be used when determining EASI and vIGA responses.

[figure not shown]
The analysis for the study overall will be conducted only for subjects who were initially randomized to any dose of SCD-044 and thus did not switch treatments during the study. In this analysis subjects will be analyzed by treatment groups based on their treatments in Part I. Times will be defined similarly to the analysis of Part I, except then will be censored at the last assessment in the study.

Quartiles of time to achieve EASI75 and EASI90, and time to achieve vIGA and PP-NRS responses with their 95% confidence intervals will be calculated by treatment group.

